7.4.2. Sustained 6-month Disability Progression in the 205MS203-303 ITT Population

Time to confirmed 6-month disability progression will be summarized for the 205MS203-303 ITT population in the 205MS303 Treatment period. For the 205MS303 Treatment Period, progression will be calculated relative to the EDSS score at the 205MS303 baseline. Subjects who do not have a sustained progression will be censored on the date of the last EDSS prior to the end date of the 205MS303 treatment period. For subjects with a tentative progression that cannot be confirmed because there are no additional EDSS assessments, the follow-up ends before a sustained progression occurs (i.e., due to the subject withdrawing from the study or due to the cutoff of data collection), or because the confirmatory assessment does not meet other criteria (i.e., the last EDSS assessment is <158 days after the tentative progression or the last EDSS assessment is at the time of a relapse), the censor date will be the date of the last EDSS assessment. Due to the limited number of subjects, no imputation will be conducted for subjects with tentative progression in the 205MS203-303 ITT population.

Time to confirmed disability progression will be explored using Kaplan-Meier method, with the first dose date in the 205MS303 Treatment period as the start date for all subjects combined. Kaplan-Meier method for time to disability progression will be used to estimate the proportion of subjects who experienced progression at selected time points for all subjects combined.

	Protocol 205MS303 Statistical Analysis Plan	Final Version 1.0
---	--	--------------------------

7.4.3. Sustained 6-month Disability Progression in the 205MS302-303 ITT Population

Time to confirmed 6-month disability progression will be summarized for the 205MS302-303 ITT population during the 205MS303 Treatment Period. Time to confirmed disability progression will be explored using Kaplan-Meier method, with the first dose date in the corresponding study period as the start date. Kaplan-Meier method for time to disability progression will be used to estimate the proportion of subjects who experienced progression at selected time points. Kaplan-Meier plots of the time to first progression will be presented and used to estimate the median time (and/or 25th percentile). Due to the limit number of subjects, no imputation will be conducted for subjects with tentative progression in the 205MS302-303 ITT population.

7.5. MSIS-29

Scoring algorithm described in Hobart J, Lamping et al. (2001) will be used to calculate the MSIS-29 Physical Impact and Psychological Impact scores. Physical score will be based on the responses from items 1-20, while psychological score is based on items 21-29. Missing scores will not be imputed. MSIS-29 physical score data obtained after subjects take alternative medication for MS during the study will be set to missing.

For the 205MS301-303 ITT population, the actual values for MSIS-29 physical score, MSIS-29 psychological score, their change from 205MS303 baseline, and the proportion of subjects with a ≥ 7.5 worsening in MSIS-29 physical score from the 205MS303 baseline will be summarized by 205MS301 treatment group in the Combined Study Period (by study visit in 205MS303 study).

Note that MSIS-29 is not collected for patients enrolled from the 205MS203 or 205MS302 study to the 205MS303 study.

7.6. MRI Endpoints

7.6.1. MRI Endpoints Analyses for the 205MS301-303 ITT Population

MRI is measured on all subjects in the 205MS301 and 205MS303 studies. Observed MRI data measured after subjects started alternative MS medications will be excluded. The following MRI parameters will be analyzed in the 205MS301-303 ITT population:

- The total number of new or newly enlarging T2 hyperintense lesions relative to the 205MS301 baseline
- The total number of new or newly enlarging T2 hyperintense lesions relative to the 205MS303 baseline
- The total number of new T1 hypointense lesions relative to the 205MS301 baseline
- The total number of new T1 hypointense lesions relative to the 205MS303 baseline
- The total number of Gd-enhancing lesions at 205MS301 study and 205MS303 study

- The total volume of T2 hyperintense lesions
- The volume of new or newly enlarging T2 hyperintense lesions compared to the 205MS301 baseline
- The volume of new or newly enlarging T2 hyperintense lesions compared to the 205MS303 baseline
- The volume of new T1 hypointense lesions compared to the 205MS301 baseline
- The volume of new T1 hypointense lesions compared to the 205MS303 baseline
- Percent Brain Volume Change (PBVC) relative to the 205MS301 baseline
- Percent Brain Volume Change (PBVC) relative to the 205MS303 baseline

Baseline:

Records up to 28 days after the first dose in 205MS301 may be used as the 205MS301 baseline assessments; If there are multiple records for the 205MS301 baseline, then the observation closest to the first dose will be selected (if tied, then the record prior to dosing will be defined as baseline). For the 205MS301 Week 96 MRI assessment, records collected up to 28 days after 205MS303 extension trial first dose will be included.

For the baseline assessment in 205MS303, the baseline MRI obtained in 205MS303 will be used as the baseline if it was obtained up to 28 days after the first dose in 205MS303. If a subject did not have a baseline MRI assessment in 205MS303, then the last assessment obtained during 205MS301 will be used at the baseline assessment for the total number of Gd-enhancing lesions and the total volume of T2 hyperintense lesions.

The total number of T2 lesions at 205MS303 baseline will be calculated by summing the 205MS301 baseline number of T2 lesions and the number of new or newly enlarging lesions since the previous visit at 205MS301 Week 24, 205MS301 Week 96, 205MS301 Week 144 (if available) and 205MS303 Baseline (if available). The same algorithm will be applied to the total number of T1 lesions and the total volume of T1 lesions at 205MS303 baseline.

Data obtained after alternative MS medication will be set to missing. Missing data will not be imputed.

The total number of new or newly enlarging T2 hyperintense lesions

The number of new or newly-enlarging T2 hyperintense lesions relative to the 205MS301 baseline will be analyzed for Week 24 and Week 96 of the 205MS301 study. The number of new or newly-enlarging T2 hyperintense lesions relative to the 205MS303 baseline will be analyzed for Weeks 48, 96, 144, 192, and 240 (if available) of the 205MS303 study.

A negative binomial regression model will be used to analyze the observed new or newly enlarging T2 lesions. The model for the analysis relative to the 205MS301 baseline will be adjusted for the following characteristics at the 205MS301 baseline: volume of T2 hyperintense lesions, history of prior IFN β use and baseline age (age \leq 35 versus age $>$ 35). The model for the analysis relative to

	Protocol 205MS303 Statistical Analysis Plan	Final Version 1.0
---	--	--------------------------

the 205MS303 baseline will be adjusted for the following characteristics: the volume of T2 hyperintense lesions at the 205MS303 baseline, history of prior IFN β use at the 205MS301 baseline, and baseline age (age \leq 35 versus age $>$ 35) at the 205MS303 baseline.

The total number of new T1 hypointense lesions

The total number of new T1 hyperintense lesions relative to the 205MS301 baseline and the 205MS303 baseline will be analyzed using the same methodology as for the analysis new or newly-enlarging T2 hyperintense lesions. The estimated number of lesions will be evaluated using negative binomial regression, adjusted for the history of prior IFN β use at the 205MS301 baseline, age (age \leq 35 versus age $>$ 35) at the corresponding baseline, and volume of T1 hypointense lesions at the corresponding baseline.

Number of Gd-Enhancing Lesions

The total number of Gd-enhancing lesions will be tabulated for the following visits of the 205MS301 study: Baseline, Week 24, Week 96 and Week 144, and for the following visits of the 205MS303 study: Baseline, Weeks 48, 96, 144, 192, and 240 (if available). Summary statistics by the 205MS301 treatment group will also be provided.

The total volume of T2 hyperintense lesions

Summary statistics for the total volume of T2 hyperintense lesions and its change from 205MS301 baseline, by 205MS301 treatment group, will be provided for Week 24, Week 96 and Week 144 of the 205MS301 study. Similar analysis will be performed for Weeks 48, 96, 144, 192, and 240 (if available) of the 205MS303 study (with change from the 205MS303 baseline).

Volume of new or newly enlarging T2 hyperintense lesions

Summary statistics for the volume of new or newly enlarging T2 hyperintense lesions, by 205MS301 treatment group, will be provided for the following visits of the 205MS301 study: Week 24, Week 96 and Week 144, and for the following visits of the 205MS303 study: Baseline, Weeks 48, 96, 144, 192, and 240 (if available).

Volume of new T1 hypointense lesions

The criteria and analysis for this endpoint will be the same as used for the volume of new or newly enlarging T2 hyperintense lesions.

Percent Brain Volume Change (PBVC)

Summary statistics for the (annualized) Percent Brain Volume Change (PBVC) relative to either the 205MS301 baseline or the 205MS303 baseline, by 205MS301 treatment group, will be provided for the Weeks 48, 96, 144, 192, and 240 (if available) of the 205MS303 study.

	Protocol 205MS303 Statistical Analysis Plan	Final Version 1.0
---	--	--------------------------

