6.2. Demography and Baseline Disease Characteristics

6.2.1. Demography and Baseline Disease Characteristics for the 205MS301-303 ITT Population

Demographic data collected at the start of 205MS301 study (205MS301 Baseline) and at the start of 205MS303 study (205MS303 Baseline) for the 205MS301-303 ITT population will be summarized by previous 205MS301 treatment group and for all subjects combined. Demographic data will include age at baseline (years), age category (<18, 18-19, 20-29, 30-39, 40-49, 50-55, and >55, also ≤ 35 , >35), gender, height, race category and weight (kg).

Medical history (collected at the start of 205MS301 and updated since) will be summarized by prior treatment group in the 205MS301 study and for all subjects combined for the 205MS301-303 ITT population. Other baseline characteristic data at 205MS301 Baseline and at 205MS303 Baseline (e.g., EDSS test scores, the number of relapses in a year prior to baseline, MRI endpoints) will also be summarized for the 205MS301-303 ITT population using descriptive statistics by 205MS301 treatment group and for all subjects combined.

EDSS test score at the 205MS303 baseline is defined as score at the most recent assessment prior to the first dose in 205MS303, excluding assessments occurring within 29 days after a relapse onset.

The following MRI characteristics will be presented for the 205MS301 baseline and the 205MS303 baseline in the 205MS301-303 ITT population: the number of Gd lesions, the number and volume of T2 hyperintense lesions, and the number and volume of T1 hypointense lesions.

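### The derived T2 lesion total at 205MS303 baseline counts newly enlarging lesions again, and the summed T1 volume used as a covariate is only an approximation

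*SAP*

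**What the plan says.** SAP section 7.6.1, under Baseline, obtains the total T2 lesion count at 205MS303 baseline by "summing the 205MS301 baseline number of T2 lesions and the number of new or newly enlarging lesions since the previous visit". The increments come from the Week 24, Week 96 and (if available) Week 144 scans of 205MS301 and from the 205MS303 baseline scan (if available). The section then extends the rule: "The same algorithm will be applied to the total number of T1 lesions and the total volume of T1 lesions at 205MS303 baseline".

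The results are used in two places:

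- Section 6.2.1 lists the MRI characteristics to be tabulated at both baselines, by 205MS301 treatment group and overall: "the number of Gd lesions, the number and volume of T2 hyperintense lesions, and the number and volume of T1 hypointense lesions".
- Section 7.6.1 adjusts the negative binomial model for new T1 lesions for "volume of T1 hypointense lesions at the corresponding baseline", together with prior IFN β use and age group.

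Two other quantities are handled differently. If a subject has no 205MS303 baseline scan, the last 205MS301 scan is "used at the baseline assessment for the total number of Gd-enhancing lesions and the total volume of T2 hyperintense lesions". These two come from an actual scan, not from a sum.

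**The concern.** A lesion scored as newly enlarging was visible at the previous visit. It is therefore already in the 205MS301 baseline count or in an earlier increment. Adding it again, once for each interval in which it enlarges, gives a figure that is not a number of lesions, and no step in the rule takes it out. A baseline row labelled as the number of T2 lesions would then be too high.

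T1 volume raises a separate issue. Adding increment volumes to the 205MS301 baseline volume treats every pre-existing T1 lesion as unchanged in size throughout 205MS301. That derived volume is both tabulated and used as an adjustment term for a secondary MRI endpoint.

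**Working it through.** The SAP gives no lesion counts, lesion volumes or share of enlarging lesions, so there is no figure to reproduce. The check is a counting identity, followed by an illustration in which every input is an assumption.

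**T2 count.** Let B be the 205MS301 baseline count, A the sum of new or newly enlarging scorings over the later scans, and f the share of A that is newly enlarging. Assume every interval is covered by a scan.

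- Count under the SAP rule: B + A
- Distinct lesions recorded: B + A(1 − f)
- Overcount: A × f, the number of enlarging scorings

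The overcount is zero only if no lesion is ever scored as enlarging. The sum also never removes lesions that disappear; that effect is left out here.

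| B | A | SAP sum | f = 0 | f = 0.10 | f = 0.25 | f = 0.50 |
|---|---|---|---|---|---|---|
| 20 | 5 | 25 | 25 (0%) | 24.5 (2.0%) | 23.75 (5.3%) | 22.5 (11.1%) |
| 20 | 10 | 30 | 30 (0%) | 29 (3.4%) | 27.5 (9.1%) | 25 (20.0%) |
| 50 | 5 | 55 | 55 (0%) | 54.5 (0.9%) | 53.75 (2.3%) | 52.5 (4.8%) |
| 50 | 10 | 60 | 60 (0%) | 59 (1.7%) | 57.5 (4.3%) | 55 (9.1%) |

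The cells under f give the distinct lesions and, in brackets, the overstatement, (B + A) / (B + A(1 − f)) − 1. For B = 20, A = 10, f = 0.25: 30 / 27.5 − 1 = 9.1%.

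**T1 volume, new lesions only added.** Let V be the 205MS301 baseline volume, n the volume of new lesions and g the relative change in the volume of existing lesions.

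- Volume under the SAP rule: V + n
- Actual volume: V(1 + g) + n

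With V = 5.0 and n = 0.5 (arbitrary units), the SAP sum is 5.5:

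- g = −20%: actual 4.5, error 5.5 / 4.5 − 1 = +22%
- g = 0: actual 5.5, error 0%
- g = +20%: actual 6.5, error 5.5 / 6.5 − 1 = −15%

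Trying V = 2.0 or 5.0 with n = 0.2 or 0.5 gives errors of +19.0% to +23.8% at g = −20%, and −13.8% to −16.1% at g = +20%.

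**T1 volume, enlarging lesions also added.** Suppose the total is 2.0 and one lesion grows from 0.5 to 0.8. Adding its full volume gives 2.0 + 0.8 = 2.8, against an actual 2.0 + 0.3 = 2.3. Here its earlier volume of 0.5 is counted twice.

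**Where each quantity goes.** The T2 model at 205MS303 baseline adjusts for "the volume of T2 hyperintense lesions at the 205MS303 baseline", which is scan-based, so the summed T2 count enters no model. The summed T1 volume does enter one.

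**The case against.** The arithmetic for the T2 count is hard to dispute. The case on the other side concerns reach, the T1 part and feasibility.

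- **Reach.** The summed T2 count is one row of a descriptive table. The T2 endpoints are counts of new or newly enlarging lesions, not this total. The primary endpoints are adverse events and serious adverse events (section 1.1), and the analyses are generally descriptive (section 5.4). This stands and limits the severity. A reader might infer that the double count biases the T2 lesion model; it does not, because that model uses T2 volume.
- **T1.** The T1 parameters listed in section 7.6.1 are for new lesions only. The natural reading of the extended rule is baseline plus new T1 lesions, so the T1 number is probably not double-counted. This also stands. A reader might infer that the T1 covariate is inflated in the same way as the T2 count. On that reading it is not: it is an approximation whose error may be positive, zero or negative.
- **Covariate effect.** T1 volume is one of three named adjustment terms in one secondary analysis. Nothing in the SAP shows how far an adjusted lesion number would move. This stands.
- **Feasibility.** The last-scan fallback is limited to Gd count and T2 volume. This suggests, without proving, that the other totals were not read after the 205MS301 baseline, which would explain the summing. It affects which remedy is possible; it does not make the sum a lesion total.

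**Conclusion.** The point holds in limited form. As written, the T2 total at 205MS303 baseline is overstated by the number of enlarging scorings over up to four scans. The SAP does not allow that number to be derived; the 0% to 20% above rests wholly on assumed values of B, A and f. It affects a descriptive table only.

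The T1 volume at 205MS303 baseline is an approximation with error of unknown direction, and it serves as a covariate in the model for new T1 lesions. The effect on that model's estimates is not established.

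A reader might also infer that the T2 overstatement differs between the former IFN β-1a and DAC HYP groups. It would if the groups differed in enlarging scorings during 205MS301, but the SAP gives no lesion data by group, so this cannot be asserted.

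Severity is minor to moderate: a baseline table and one secondary-endpoint covariate, with the primary safety endpoints untouched.

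**What to change.** In section 7.6.1, under Baseline:

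1. Where the T2 count, T1 count or T1 volume was read as a total on the 205MS303 baseline scan, or else on the last 205MS301 scan, use that reading, as the SAP already does for T2 volume and Gd count.
2. Where only increments exist, add new lesions only.
3. If new and enlarging lesions cannot be separated, do not call the sum a total number of lesions. Report it as the 205MS301 baseline count plus cumulative new or newly enlarging lesions, and use the same label in the section 6.2.1 table.
4. State explicitly whether the T1 increments are new lesions only.
5. Use measured T1 volume as the model covariate where it exists; where it does not, label the summed volume as derived.

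The cost is a change of SAP wording, one derivation and some table labels. The drawback is that measured totals may be missing for some or all subjects, in which case only the relabelling and the new-lesions-only options remain.

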7.6.2. MRI Endpoints Analyses for the 205MS203-303 ITT Population

For the 205MS203-303 ITT population, MRI was not collected at 205MS303 baseline, and most of the subjects only have one MRI visit in the 205MS303 study. By visit summary will be presented for selected parameters including the total number of Gd-enhancing lesions, and the total volume of T2 hyperintense lesions. Note that due to the timing of implementation of protocol version 4, there is very limited data available for other MRI parameters and therefore these will not be summarized.

7.6.3. MRI Endpoints Analyses for the 205MS302-303 ITT Population

For the 205MS302-303 ITT population, MRI was not collected at 205MS303 baseline, and most of the subjects only have one MRI visit in the 205MS303 study. By visit summary will be presented for the selected parameters, including the total number of Gd-enhancing lesions, and the total volume of T2 hyperintense lesions. Note that due to the timing of implementation of protocol version 4, there is very limited data available for other MRI parameters and therefore these will not be summarized.

7.7. EDSS

7.7.1. EDSS in the 205MS301-303 ITT Population

For the 205MS301-303 ITT population, the EDSS score with change from 205MS303 baseline will be summarized by 205MS301 treatment group in the 205MS303 Treatment Period (by study visit in 205MS303 study).

7.7.2. EDSS in the 205MS203-303 ITT Population

For the 205MS203-303 ITT population, the EDSS score with change from 205MS303 baseline will be summarized in the 205MS303 Treatment Period (by study visit in 205MS303 study) for all subjects together.

7.7.3. EDSS in the 205MS302-303 ITT Population

For the 205MS302-303 ITT population, the EDSS score with change from 205MS303 baseline with change from 205MS303 baseline will be summarized by study visit in 205MS303 for all subjects together.

7.8. EQ-5D

The EQ-5D is a generic health-related quality of life (QoL) instrument which has been extensively validated. There are two components to the EQ-5D used in this protocol, a Health State Profile and a Visual Analog Scale (VAS). With the Health State Profile, patients record their level of current health for five domains comprising a health profile: mobility, self-care, usual activities, pain/discomfort, and anxiety/depression. A score of 1, 2, or 3 are possible responses for each of the five questions in the Health State Profile (1=no problems, 2=some problem, 3=severe problems). With the Visual Analogue Scale (VAS), patients are asked to rate their current health on a 20 cm scale from 0 to 100

	Protocol 205MS303 Statistical Analysis Plan	Final Version 1.0
---	--	--------------------------

where 0 represents “worst imaginable health state” and 100 represents “best imaginable health state”. The EQ-5D summary index score will be computed from the Health State Profile using MVH A1 Tariff (Dolan, 1997). Missing values will not be imputed. The EQ-5D summary index score data obtained after subjects take alternative medication for MS during the study will be set to missing.

7.8.1. EQ-5D in the 205MS301-303 ITT Population

For the 205MS301-303 ITT population, the EQ-5D Health State Profile scores, the EQ-VAS scores with change from 205MS303 baseline, and the summary index scores with change from 205MS303 baseline will be summarized for the 205MS301-303 ITT population by 205MS301 treatment group and by study visit in 205MS303.

7.8.2. EQ-5D in the 205MS203-303 ITT Population

For the 205MS203-303 ITT population, the EQ-5D Health State Profile scores, the EQ-VAS scores with change from 205MS303 baseline, and the summary index scores with change from 205MS303 baseline will be summarized for all subjects combined in the 205MS303 Treatment Period (by study visit in 205MS303 study).

7.8.3. EQ-5D in the 205MS302-303 ITT Population

For the 205MS302-303 ITT population, the EQ-5D Health State Profile scores, the EQ-VAS scores with change from 205MS303 baseline, and the summary index scores with change from 205MS303 baseline will be summarized by study visit in 205MS303.

7.9. Health Resource Utilization (HRU)

7.9.1. HRU in the 205MS301-303 ITT Population

For the 205MS301-303 ITT population, the total number of unscheduled site visits per collection time will be summarized separately for MS-related and non-MS related visits. Summaries will be presented by 205MS301 treatment group in the 205MS301 Treatment Period and the 205MS303 Treatment period. The annualized rate of unscheduled site visits will be calculated as the total number of unscheduled visits collected on Patient Health Care Treatment CRF page, divided by the total number of years.

7.9.2. HRU in the 205MS203-303 ITT Population

For the 205MS203-303 ITT population, the total number of unscheduled site visits per collection time will be summarized separately for MS-related and non-MS related visits. Summaries will be presented for all subjects combined in the 205MS303 Treatment period. The annualized rate of unscheduled site visits will be calculated as the total number of unscheduled visits collected on Patient Health Care Treatment CRF page, divided by the total number of years.

	Protocol 205MS303 Statistical Analysis Plan	Final Version 1.0
---	--	--------------------------

